### **9.3 Concomitant Medications**

Medication use from consent through EOS will be coded to generic terms using the World Health Organization Drug Dictionary (WHO-DD), version June 1, 2016. Listings will include IP administration date, WHO-DD drug class, WHO-DD preferred drug name, generic/trade drug name, start and stop dates, dose, route, frequency, indication, and associated AE and SAE number, if applicable. Frequencies and percentages of subjects reporting or receiving each medication will be summarized by WHO-DD drug class and preferred name within drug class. Any pre-infusion/reference date medications reported will be listed and summarized separately from concomitant medications. Cardiac and steroid medications will also be listed and summarized separately. Medications that were stopped no later than the day before IP administration or reference day will be considered “pre-infusion.” All other medications will be considered “concomitant.” Medications recorded with insufficient exposure dates to determine whether or not they were concomitant will be considered concomitant.

### **9.4 Safety Laboratory Evaluations**

Specific laboratory evaluations to be performed are detailed in Appendix 2 of the protocol. Listings of safety laboratory evaluations will include study visit, date and time of collection, normal ranges, observed values with out-of-range values flagged, and changes from baseline. Separate series of listings will show out-of-range observations.

Observed values and changes from baseline will be summarized by study visit. A separate series of summaries will show incidence of out-of-range observations by study visit. Shift tables will summarize shifts from one out-of-range category at baseline to another out-of-range category at each subsequent study visit and will include p-values for treatment group differences.

Listings and summaries will be done separately for each of the following laboratory evaluations or groups of evaluations:

- Serum chemistry (basic metabolic and comprehensive hepatic panels)
- Hematology
- Urinalysis
- Glycosylated hemoglobin (HbA1c)
- Cardiac (troponin I, troponin T, CK-MB)
- Immunogenicity (HLA, DSA, enzyme-linked immunosorbent spot (ELISPOT))
- Exploratory biomarkers, if available

For DSA, the raw data will be provided by the core laboratory and a listing of HLA antibodies and specific alleles will be provided to the independent clinical immunologist to make the final determination of which are DSA caused by sensitization to the donor cells, and which are non-specific changes that are not due to donor-specific sensitization. Any summary tables or analyses of DSA will be based on DSA as adjudicated by the independent clinical immunologist.

The results of the ELISPOT assay for the tested samples will be reported as number of spots/400,000 cells/well. In addition, the results will be expressed as mean and standard deviation (SD) of the triplicate (or duplicate) wells for serum-free medium wells, fetal bovine serum (FBS)-containing medium wells, and antigen-stimulated wells. For phytohemagglutinin (PHA)-stimulated wells the result will be the spot number/400,000 cells from the single well. If the cell number would be insufficient and the testing will be performed in a single well for a given variant, then the result will be the spot number/400,000 cells from the single well. A positive or negative response to each antigen (cardiac cell lines) will be determined based on the results of each individual sample. A positive response will be defined as greater than  $Y + 2SD$  of  $Y$  number of spots after exposure to Antigen (X) and more than 10 spots, whereby:

Y: Average spot number in the FBS-medium control (cells and no antigen)

X: Average spot number to the given antigen (cells and antigen)

The antigen specific response = antigen positive response =  $X - (SD \text{ of } X) - [Y + (2SD \text{ of } Y)]$  and has to be greater than the numerical value 3. All negative values generated by the formula above will be reported as 0 spot values, as negative values are biologically irrelevant.

The results for the control sample will be reported as number of spots/400,000 cells/well. In addition, the results will be expressed as mean and SD of the triplicate wells for medium wells, antigen-stimulated wells and PHA wells.

Any clinical sample that will produce below 100 interferon-gamma spots in response to the mitogen (positive control) PHA will be flagged as non-functional and the ELISPOT results for that sample should be excluded from further analysis.

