**Study Design:**

Male subjects at least 12 years of age, with cardiomyopathy secondary to DMD, and meeting all inclusion and no exclusion criteria, will be randomized. Each subject that meets all eligibility criteria will be randomized in a 1:1 manner to either investigational product (CAP-1002) or usual care.

If randomized to investigational product, a subject will receive an intracoronary infusion of CAP-1002 (intended total dose of 75 million [75M] cells) in three coronary arteries supplying the three major cardiac territories of the left ventricle of the heart (anterior, lateral, inferior/posterior). All three major cardiac territories will be treated (infused) during a single procedure in an open-label fashion.

Subjects randomized to receive usual care will not receive an infusion. They will continue to be cared for and treated in whatever manner the investigator deems most appropriate for the subject on an ongoing basis, except that usual care cannot include treatment with CAP-1002 or other investigational treatments.

Approximately 24, and not more than 30, subjects will be randomized into the study in two sequential enrollment groups. Safety data from Group 1 will undergo a Data Safety Monitoring Board (DSMB) review prior to initiation of enrollment for Group 2.

The first 6-8 randomized subjects will comprise Group 1, and will include a minimum of 3 subjects completing intracoronary infusion with CAP-1002. The DSMB will conduct a review of interim safety data through 72 hours post -Day 0 for at least 3 infused subjects and for at least 6 subjects overall.

Enrollment of Group 2 will begin per DSMB recommendations following their review of the 72 hour safety data from Group 1. Group 2 will include approximately 18 subjects.

Screening and randomization will continue until at total of 12 subjects are infused with CAP-1002 or 30 subjects are randomized into the study, whichever comes first.

CCI

Subject infusions will be staggered by at least three days to allow for detection of acute procedure-related complications should they occur. Additionally, subject infusions in Group 2 will not begin until at least two weeks after the final infusion occurs in Group 1, to allow for completion of the Group 1 safety data review through 72 hours post Day 0.

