g) Development of increased anti human leukocyte antigen (HLA) antibody levels with development of sensitization to HLA antigens specific to the CAP-1002 CDC donor. Elevation of donor-specific antibodies (DSA) is defined as mean fluorescence intensity (MFI) above a threshold of 5000; a threshold of 1000 MFI will also be used to evaluate elevation of DSA. See [Section 9.1](#) for details related to comparison between CAP-1002 and usual care subjects.

2) Adverse events (AEs)

3) Concomitant medications

4) Change from baseline in laboratory evaluations

5) Peak elevation in troponin and CK-MB levels following IP infusion or on reference date

- 6) Changes from baseline in vital signs, weight, and body mass index (BMI)
- 7) Changes from baseline on general and cardiac physical examinations
- 8) Changes from baseline in electrocardiogram (ECG), both 12-lead ECG and continuous cardiac monitoring

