### 9.1 Adjudicated Clinical Events

Clinical events, described in [Section 2.3.1](#), will be adjudicated by an independent Clinical Events Committee (CEC) (see [Section 12](#)). Each event will be summarized as frequency and percentage of subjects who experienced the event. In addition, a composite event will be defined as new TIMI flow 0-2 or TMPG 0-2 (CAP-1002 subjects only), sudden death, or MACE during or following IP administration or reference time point. For the composite and its components, summaries will include exact 90% confidence intervals (CIs) for both treatment groups. For peri-procedural events other than TIMI flow 0-2 or TMPG 0-2, summaries will include a 90% CI for the difference in proportions between treatment groups, and the one-sided p-value from an exact binomial test of the difference between treatment groups. For all other clinical events, assessed over the length of the trial, event rates per 100 subject-years will be calculated and, if applicable, treatment groups will be compared using negative binomial regression with an offset for days of follow-up (log transformed). If the dispersion parameter is not significantly different from zero, Poisson regression will be used instead.

For the analysis of development of increased HLA antibodies to HLA antigens specific to the CAP-1002 donor, incidence of increased HLA antibody levels specific to the donor will be summarized and analyzed; for usual care subjects, a random donor will be selected from those that were matched to the subject during screening. Elevated levels of donor specific antibodies will also be summarized and analyzed by time point for all nominal time points at which samples were collected for DSA testing. Analyses will be performed using both 1000 and 5000 MFI as the threshold for defining increased HLA antibodies.

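### SAP 9.4's causal test for donor-specific antibody, with no masking stated, can empty the random-donor control that SAP 9.1 sets up

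*SAP*

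**What the plan says.** SAP 2.3.1 lists development of donor-specific HLA antibody among the safety assessments and sends the reader to SAP 9.1 "for details related to comparison between CAP-1002 and usual care subjects".

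SAP 9.1 sets up the control: "for usual care subjects, a random donor will be selected from those that were matched to the subject during screening". It also gives a numerical rule: "Analyses will be performed using both 1000 and 5000 MFI as the threshold for defining increased HLA antibodies".

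SAP 9.4 adds a layer of judgement. On the reader's material it says: "a listing of HLA antibodies and specific alleles will be provided to the independent clinical immunologist". The task is "to make the final determination of which are DSA caused by sensitization to the donor cells". Whatever the reader does not attribute in this way falls into a second category: "which are non-specific changes that are not due to donor-specific sensitization". The scope is general: "Any summary tables or analyses of DSA will be based on DSA as adjudicated by the independent clinical immunologist". No exception is made for the comparison in 9.1.

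On exposure, the Protocol synopsis (Study Design) says: "Subjects randomized to receive usual care will not receive an infusion". SAP 6 analyses the safety population by treatment received.

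On masking, SAP 10.1 states it for the MRI overreaders and SAP 13.2.2 for the imaging core laboratory. Nothing comparable is stated for the immunologist, who is described only as independent.

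**The concern.** A random donor for an unexposed subject has one evident use: to show how often antibody against a given donor rises without any cells having been given. That background rate is what the CAP-1002 rate should be set against. A criterion that asks whether the donor cells caused the antibody excludes, on its literal wording, anyone who received none. If the reader knows the arm, usual-care rises go into the non-specific category because of the arm and not because of the antibody pattern, while CAP-1002 rises are judged case by case. The two arms are then measured by different rules.

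Safety is the primary objective, the product is allogeneic, and the trial is open-label, so arm is not hidden by design. The loss would be the ability to tell sensitization from background fluctuation.

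**Working it through.** The plan gives no expected DSA rate and no power for this comparison, so there is no figure to reproduce. The check has two parts.

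**1. The sections side by side**

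- SAP 9.1: usual-care subjects are counted against an assigned random donor, at two MFI thresholds.
- SAP 9.4: what counts as DSA, in any table or analysis, is what the reader attributes to donor cells.
- Protocol and SAP 6: nobody in the usual-care safety group was exposed to donor cells.

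Taken literally together, the second and third leave the first with a usual-care count of zero, unless the reader is masked or the criterion is read as one of specificity only.

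**2. Size, under stated assumptions**

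Inputs from the documents: about 12 subjects per arm (SAP 4); two-sided 0.05 and Fisher's exact test when a cell is below 5 (SAP 7.3). Assumptions: no product effect, and the same background rate q of new antibody against the assigned donor in both arms. A fraction a_C of these rises in the CAP-1002 arm, and a_U in usual care, is called caused by the cells.

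Expected difference = q × (a_C − a_U).

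- Masked reader, same rule in both arms: a_C = a_U, so the difference is 0.
- Arm-aware reader applying 9.4 literally: a_U = 0, so the difference is q × a_C, between 0 and q. At q = 10% that is 0 to 10 points; at q = 20%, 0 to 20 points.
- Expected usual-care rises reclassified as non-specific: 12 × 0.10 = 1.2 and 12 × 0.20 = 2.4.

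Smallest CAP-1002 count reaching p ≤ 0.05 by Fisher's test:

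- against 0/12: 5/12 (p = 0.037; 4/12 gives 0.093);
- against 1/12: 7/12 (p = 0.027);
- against 2/12: 8/12 (p = 0.036).

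With usual care at 0/12, the chance of a spurious significant excess is P(X ≥ 5), X ~ Binomial(12, q × a_C). The last column is the chance of a significant CAP-1002 excess when a masked reader counts all rises in both arms.

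| Assumed q | Arm-aware, a_C = 1 | Arm-aware, a_C = 0.5 | Masked, all counted |
|---|---|---|---|
| 10% | 0.4% | 0.02% | 0.1% |
| 20% | 7.3% | 0.4% | 0.6% |
| 30% | 27.6% | 2.4% | 0.9% |
| 40% | 56.2% | 7.3% | about 1% |

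If the negative binomial or Poisson model in SAP 9.1 is used instead of Fisher's test, a zero count in one arm leaves the rate ratio without a finite estimate.

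These figures cover background rises only. They do not model real sensitization wrongly dismissed as non-specific in the CAP-1002 arm.

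**The case against.** The strongest reply is that the two sections can be reconciled. The contrast drawn in 9.4 is between donor-specific and non-specific change, judged from a list of antibodies and alleles. That can be a call on specificity pattern, which can be made against any assigned donor, random or real. Section 9.1 makes sense only if usual-care subjects can be classified in this way. This stands as a possible reading, and it is why one cannot say that a positive usual-care subject is ruled out by definition. It is not what 9.4 literally asks, however, and the SAP should not leave the choice to the reader.

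A reader might also infer that the immunologist is unmasked. The documents do not say so. They describe a listing of antibodies and alleles and mention no treatment column. The gap is a safeguard left unstated, so a zero usual-care rate is a risk and not an established consequence.

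A reader might further infer that the difference is inflated by the whole background rate. That needs every background rise in the CAP-1002 arm to be attributed to the cells. If the reader correctly removes non-specific rises in both arms, there is no inflation: zero is then the true usual-care count of antibody caused by cells.

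Three further points stand. The background may be low, because the random donor comes from donors against whom the subject had no antibody at screening (Protocol 1.3), so a usual-care positive needs a new rise. The control values are not lost, since SAP 7.2.2 and 7.5 list data as reported and SAP Appendix B plans a DSA listing (16.2.8.8). And immunologist review has a proper purpose in filtering out non-specific signal, so the adjudicated result should stay.

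**Conclusion.** The point holds as an unresolved conflict between SAP 9.1 and 9.4, made worse by silence on masking. Applied literally by someone who knows the arm, the 9.4 criterion can bring the usual-care rate to zero and leave the random-donor comparison without information on background.

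With no product effect, the bias in the difference runs from 0 to the background rate: 0 to 20 points across an assumed 10–20%. That range is an assumption without support in the documents. In the worst case for attribution, the chance of a spurious significant excess is 0.4% at 10% background and 7.3% at 20%; it becomes material only at higher rates. At low background the main harm is therefore an uninformative control rate and a difference that may be biased upward, not a false positive test. Minor priority.

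**What to change.** Three changes are needed together; hiding the arm alone would neither repair the causal wording nor conceal which donors are random.

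1. In SAP 9.1, report the between-arm incidence by the existing 1000 and 5000 MFI rule against the assigned donor in both arms, without adjudication, alongside the adjudicated result. Exempt this analysis from the general sentence in 9.4.
2. In SAP 9.4, make the criterion exposure-neutral: new antibody specific to the assigned donor's HLA, versus non-specific change.
3. Fix each usual-care subject's random donor before adjudication, show it in the same format as an actual donor, and withhold arm and infusion status from the immunologist's listing. State this masking in the SAP.

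The cost is a few sentences of SAP text, a change to the listing and one additional presentation of data already collected. It needs no extra subjects, samples or reader: a free improvement.

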## 9.5 Vital Signs, Height, Weight, and BMI

Vital signs will include systolic and diastolic blood pressure, heart rate, respiratory rate, and body temperature. Listings of vital signs, height, weight, and BMI will include study visit, date and time of collection, observed values, and changes from baseline. Observed values and changes from baseline will be summarized by study visit. BMI will be calculated as:

$$BMI = \frac{weight\ (kg)}{(height\ (m))^2}$$

## 9.6 Physical Examination

General and cardiac physical examination findings will be listed and summarized separately. General physical examination findings will be summarized either as frequencies of normal/abnormal indicators at each visit or, if appropriate (i.e., if data are not too sparse), as shifts from baseline in normal/abnormal indicators for each body system. For cardiac physical examination findings, the number of subjects with each condition and other condition-specific details will be summarized; shifts from baseline in present/absent and normal/abnormal indicators will also be summarized, as will murmur grade.

## 9.7 12-Lead ECG and Continuous Cardiac Monitoring

Listings of 12-lead ECG parameters will include study visit, date and time of ECG, and observed values. Observed values and changes from baseline in ventricular rate and interval parameters (QRS, PR, QT, QTc) will be summarized by study visit. Overall interpretation of 12-lead ECG will also be summarized.

Listings of continuous cardiac monitoring parameters will include study visit, start and stop date/time, and observed values. Observed values and changes from baseline in QRS complexes, paced QRS complexes, ventricular ectopic beats, supraventricular ectopic beats, heart rates, and longest RR will be summarized by study visit. Presence of atrial fibrillation, including number of episodes and longest run, will also be summarized.

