**Table 3. Per-Visit Minimum Continuous Cardiac Monitoring Durations**

Study Visit	Minimum Continuous Monitoring Duration
Screening	24 hours
Day 1	72 hours
Week 6	72 hours
Month 6	7 days
Month 12	72 hours

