## Appendix 4      Amendment 3 Changes (Protocol Version 18 July 2016)

The following table presents a complete list of content changes in this protocol amendment. To avoid redundancy, the “sections affected” column does not list the protocol synopsis as an affected section.

Description of Change	Rationale/Justification	Sections Affected
Study Assessments		
“24-hour ambulatory ECG monitoring” is replaced by “continuous cardiac rhythm monitoring” for 7 days at Month 6, and for 72 hours at Day 1, Week 6, and Month 12.	The protocol already provided for non-invasive cardiac event monitoring at these time points as a key safety assessment. The duration for each of these monitoring assessments is being extended to provide additional information on the frequency and intensity of arrhythmias in DMD patients with cardiomyopathy.	Synopsis 3.3 Safety Monitoring 6.7 Portable ECG Monitor 7.1 Screening Visit 7.2 Randomization and Day 0 7.5 Week 6 Visit
“ambulatory ECG monitoring via Holter Monitor or ZIO® Patch” is replaced by “sponsor-supplied continuous cardiac rhythm monitoring”.	Previously, the ambulatory ECG monitoring system was determined by the standard of care at the study site. With the decision to extend the duration of the cardiac monitoring assessments, the sponsor will provide monitoring devices to ensure consistency of assessments at all study sites.	7.7 Month 6 Visit 7.8 Month 12 Visit Appendix 1 Schedule of Events
Clarifications/Corrections		
Events “Post-Infusion” are now divided to “Post-Infusion (D0-D1)” versus “Pre-Hospital Discharge (D1)”	This editorial change is made to clarify the separation of in-hospital ECG monitoring on Day 0 (for CAP-1002 patients only) versus 72-hour continuous cardiac rhythm monitoring on Day 1 (for all patients).	7.2 Randomization and Day 0
Total dose received is 62.5M cells, not 67.5M cells as stated previously, for special cases where infusion of 12.5M cells for that cardiac territory is warranted rather than the usual dose of 25M cells.	Correction to arithmetic error in prior versions of the protocol. In cases where the infusing Investigator deems that one of the three coronary arteries supplies less than 30% of the left ventricular myocardium, the infusing Investigator may choose to infuse only 12.5M cells into that coronary artery or arteries.	Synopsis 3.1 Overall Study Design and Plan 5.1.1 CAP-1002 Dosing Considerations

Description of Change	Rationale/Justification	Sections Affected

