## PREFACE

The purpose of this statistical analysis plan (SAP) is to describe the planned statistical analyses and reporting for Capricor Protocol CAP-1002-DMD-01 (HOPE). The planned analyses identified in this SAP may be included in future manuscripts. Exploratory analyses not necessarily identified in this SAP may be performed to support planned analyses. Any post-hoc or unplanned analyses not specified in this SAP will be clearly identified as such in the Clinical Study Report (CSR) and manuscripts for publication.

The SAP is a supplement to the study protocol, which should be referred to for additional details on study design, study conduct, and other operational aspects of the study.

The structure and content of the SAP provides sufficient detail to meet the requirements identified by the Food and Drug Administration and International Conference on Harmonisation (ICH) E9: Guidance on Statistical Principles in Clinical Trials. All work planned and described in the SAP will follow internationally accepted guidelines published by the American Statistical Association. The following documents were also considered in preparation for writing this SAP:

- Clinical Research Protocol CAP-1002-DMD-01, Amendment 3.0, July 18, 2016
- ICH E3 Guideline: Structure and Content of Clinical Study Reports
- ICH E6 Guideline on Good Clinical Practice
- ICH E8 General Considerations for Clinical Trials

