## 7.6 Study Period and Time Point Definitions

The following study periods and time points are defined:

Screening Period: the 30-day time period before IP infusion or the reference time point.

Baseline: for a given parameter for a given subject, the last observation before IP infusion or the reference time point.

Day 0: for a given subject, the day of planned IP infusion or the reference day.

(Nominal Visit) Analysis Time Point: analysis based on data collected at the *(nominal visit)* time point, where nominal visits are as shown below in [Section 7.7](#).

End of Study (EOS), Subject Level: subject-level EOS is reached after completion of the Month 12 visit or discontinuation for any reason.

EOS, Study-Level: EOS is reached when all randomized subjects have either completed the Month 12 visit or have discontinued from the study for any reason.

Long-Term Follow-Up (LTFUP) Period, Subject-Level: the LTFUP period begins after completion of the Month 12 visit and continues until 4 more annual visits have been completed.

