## 14. DSMB

The DSMB will be appointed by the sponsor and will consist of physicians and at least one biostatistician who have no formal involvement or conflict of interest with the subjects, the sponsor, the investigators, or the clinical sites. The DSMB will communicate their findings directly to the sponsor.

Data on the following, in the form of TFLs and/or narratives, will be provided to the DSMB for review:

- Subject disposition
- Demographic and other baseline characteristics
- IP administration details
- Clinical event endpoints
- Treatment-emergent AEs and SAEs
- Safety laboratory evaluations
- Concomitant cardiac and steroid medications
- Continuous cardiac monitoring

In addition, the DSMB will be provided with TFLs from the Month 6 administrative interim efficacy analysis.

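### SAP 9.7 reports rhythm-monitor counts and extremes as change from baseline with no allowance for recording time, although minimum recordings are 24 hours at baseline and 72 hours or 7 days at follow-up

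*SAP*

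**What the plan says.** Protocol section 6.7, in the table titled "Per-Visit Minimum Continuous Cardiac Monitoring Durations", requires at least 24 hours at screening, 72 hours at Day 1, Week 6 and Month 12, and 7 days at Month 6. The visit sections (7.1, 7.2, 7.5, 7.7 and 7.8) agree. Protocol Appendix 4 gives the reason for the longer follow-up recordings: "The duration for each of these monitoring assessments is being extended to provide additional information on the frequency and intensity of arrhythmias". The screening recording stayed at 24 hours.

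SAP 7.6 defines baseline as "for a given parameter for a given subject, the last observation before IP infusion or the reference time point". The screening recording is the only monitor recording scheduled before Day 0, so it is the baseline.

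SAP 9.7 then summarizes, by visit, "Observed values and changes from baseline in QRS complexes, paced QRS complexes, ventricular ectopic beats, supraventricular ectopic beats, heart rates, and longest RR". It adds: "Presence of atrial fibrillation, including number of episodes and longest run, will also be summarized". Recording time appears only in the listings: "Listings of continuous cardiac monitoring parameters will include study visit, start and stop date/time, and observed values". SAP 7.3, 7.5, 7.7 and 9.7 give no rate per recorded time, no common window and no other rule for unequal lengths.

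The SAP's Preface names its source as "Clinical Research Protocol CAP-1002-DMD-01, Amendment 3.0, July 18, 2016", the version with the unequal durations. Yet SAP Appendix A still shows a 24-hour Holter or ZIO recording at each monitored visit, and SAP 2.3.1(f) still names those devices.

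**The concern.** Safety is the primary objective. SAP 2.3.1 item 8 makes change from baseline in continuous monitoring a safety assessment, and SAP 14 lists "Continuous cardiac monitoring" among the data sent to the DSMB. A quantity that grows with recording time will appear to rise from a 24-hour baseline to a 72-hour or 7-day follow-up even if the rhythm has not changed. A reader could take that rise for a late arrhythmia signal, or could dismiss a real rise as artifact.

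The variables behave differently. Longest RR, longest AF run and any minimum or maximum heart rate are extremes over the recording, so they depend on its length whatever the device's output format. The chance of seeing any AF also grows with length. QRS, paced QRS and ectopic-beat counts and the number of AF episodes depend on length if they are totals. They do not if the device already reports them per hour or per day, and the documents do not say which. A mean heart rate is not affected, but SAP 9.7 does not say which heart rates it means.

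A related matter concerns ventricular tachycardia (VT). SAP 2.3.1(f) counts an increase in the frequency of VT without giving a time base. SAP 9.1 says that rates per 100 subject-years will be calculated for trial-long clinical events, with log days of follow-up as the offset where a regression is fitted. This VT, however, is ascertained only while the monitor is worn.

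**Working it through.** The plan states no figure on this point, so there is none to reproduce. The inputs are the Table 3 minimum durations: 1 day at screening, 3 days at Day 1, Week 6 and Month 12, and 7 days at Month 6. The first set of results assumes that every recording lasts exactly its minimum. Because the durations are minimums, a second set assumes a 48-hour screening recording; that length is not in the documents.

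**Extremes.** Let the baseline cover b days and the follow-up k days, all exchangeable (no true change, no ties). The overall maximum is equally likely to fall on any of the b + k days, so P(follow-up maximum > baseline maximum) = k/(k + b). A simulation of 400,000 pairs with b = 1 gave 50.1%, 75.0% and 87.5% for k = 1, 3 and 7.

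**Counts, if totals.** At a constant rate, relative change = k/b − 1.

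| Follow-up | Screening 24 h: P(max higher) | Screening 24 h: total count | Screening 48 h (assumed): P(max higher) | Screening 48 h (assumed): total count |
|---|---|---|---|---|
| Same length as screening | 1/2 = 50% | 0% | 1/2 = 50% | 0% |
| 72 h (k = 3) | 3/4 = 75% | 3/1 − 1 = +200% | 3/5 = 60% | 3/2 − 1 = +50% |
| 7 days (k = 7) | 7/8 = 87.5% | 7/1 − 1 = +600% | 7/9 = 78% | 7/2 − 1 = +250% |

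On totals at minimum durations, Month 6 to Month 12 would show an apparent change of 3/7 − 1 = −57%.

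**Size of the shift in a maximum.** If daily maxima are taken as independent and normal (an assumption), a simulation of 1,000,000 draws puts the expected maximum 0.85 SD higher over 3 days and 1.35 SD higher over 7 days than over 1 day. The documents give no SD, so this cannot be put into milliseconds.

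**Between arms.** An unchanged subject with daily rate r shows an expected change in total of r(k − 1) when b = 1. The arm difference in mean change is therefore (k − 1) times the arm difference in mean r. Under randomization that averages zero. In one small trial, however, a chance difference in underlying rate is carried into the change score with multiplier 2 (72 h) or 6 (7 days), where equal windows would give 0. This is how the problem would enter a default SAP 7.3 t-test on changes.

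**VT denominator.** Recorded follow-up at minimum durations is 3 + 3 + 7 + 3 = 16 days. The Month 12 recording starts at about Day 360 and runs 3 days, so the recorded share is 16/363 = 4.4%. For a subject who leaves just after the Month 6 recording it is (3 + 3 + 7)/187 = 7.0%, and just after the Week 6 recording (3 + 3)/43 = 14.0%, leaving out any early-termination recording. The share falls with longer retention, so days of follow-up are not proportional to the time in which this VT could be detected.

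**The case against.** The strongest reply is that both arms follow one schedule, so the randomized usual-care arm carries the same artifact and the comparison between arms stays fair on average. That stands. A reader might infer that the unequal recordings bias the safety comparison against CAP-1002, or in its favor. The documents do not support that: length alone gives no average between-arm difference. Only unequal wear time or retention would produce one. Unequal wear is possible, since the durations are minimums and the trial is open-label, but nothing in the documents shows it.

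Second, the count units are unknown. That also stands. A reader might infer that a Month 6 peak in ectopic beats is certain. It follows only if the device reports totals. The dependence on length is certain only for the extremes and for whether any AF is seen.

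Third, the percentages need exact recording lengths. That is correct, hence the 48-hour column. A longer screening recording shrinks the effect; longer follow-up recordings enlarge it.

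Fourth, these are supporting summaries, the named safety events are adjudicated separately, start and stop times are listed, and nothing shows that the DSMB would be denied recording lengths. This limits the weight of the point but does not repair the summaries, which report the quantities that depend on length. Nor can the point be set aside because SAP 9.7 names no test: SAP 7.3 applies t-tests or analysis of covariance to continuous variables unless Sections 8–10 say otherwise, and 9.7 states no exception.

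Fifth, on SAP Appendix A's 24-hour recordings, 9.7 would be coherent. That is probably where the mismatch began, but the appendix conflicts with the protocol version that the SAP cites.

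**Conclusion.** The point holds in this limited form. Followed as written, SAP 9.7 produces changes from baseline that partly measure recording length: for the extremes in any case, and for the counts if they are totals. At minimum durations with exchangeable days, an unchanged subject's maximum exceeds baseline with probability 75% or 87.5% instead of 50%, and totals rise by 200% or 600%. With an assumed 48-hour screening recording these fall to 60%, 78%, 50% and 250%.

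The damage is to within-arm change and to reading across visits, with added noise if wear time differs, and it carries into any default test on these data.

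The VT denominator is a secondary matter. SAP 9.1 commits to calculating the rates, so it is not hypothetical, but the effect largely cancels between arms unless retention or wear time differs. It would be wrong to read it as showing a biased VT comparison. The SAP should be corrected on both matters; neither undermines the trial's safety comparison.

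**What to change.** In SAP 9.7:

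- Express QRS, paced QRS and ectopic-beat counts and the number of AF episodes per 24 hours of recording before computing observed values and changes. Use the listed start and stop times, or analyzable time if the device supplies it.
- State which heart rates are meant. Report longest RR, longest AF run, any minimum or maximum heart rate and presence of AF with recording length beside them, and read them against concurrent usual care. Dividing by time does not correct an extreme.
- Optionally, if time-stamped output exists, add a first-24-hour value for the comparison with baseline.

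In SAP 2.3.1(f), define an increase in VT frequency per recorded time. Under SAP 9.1, use recorded time as the denominator, and its log as the offset, for any VT rate. Keep the full recordings as the main assessment of new VT. Reconcile SAP Appendix A and the Holter/ZIO wording in 2.3.1(f) with Protocol Amendment 3.

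The cost is SAP wording and a little more analysis work, with no new procedures. Start and stop times give elapsed rather than analyzable time, so some error remains. First-24-hour values would use only 4 of the 16 minimum recorded follow-up days (25%), which is why they can supplement the full recordings but not replace them.
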